#### **9.7.3.2               Secondary Effectiveness Endpoints**

The secondary effectiveness endpoints are:

- The percentage of patients with virological response (HCV RNA  $<50$  IU/mL) at EoT
- The percentage of patients with relapse (defined as HCV RNA  $<50$  IU/mL at EoT followed by HCV RNA  $\geq 50$  IU/mL)

---

Confidential Information

No use or disclose outside AbbVie is permitted without prior written authorization from AbbVie  
The Netherlands v 1.4 (26 March 2018). Protocol based on AbbVie shell protocol version 3.0 (22 April 2015) Page 36 of 65

- The percentage of patients with breakthrough (defined as at least one documented HCV RNA <50 IU/mL followed by HCV RNA ≥50 IU/mL during treatment).
- The number and percentage of patients meeting each and any of the following SVR12 non-response categories:
  - On-treatment virologic failure (breakthrough [defined as above ] or failure to suppress [each measured on-treatment HCV RNA value ≥50 IU/mL])
  - Relapse (defined as HCV RNA <50 IU/mL at EoT or at the last on-treatment HCV RNA measurement followed by HCV RNA ≥50 IU/mL post-treatment)
  - Premature study drug discontinuation with no on-treatment virologic failure
  - Missing SVR12 data and/or none of the above criteria

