#### **9.7.3.3 Statistical Methods for Analysis of Effectiveness Variables**

The simple percentage of patients achieving SVR12 will be calculated and an exact two-sided 95% confidence interval (CI) of the percentage will be computed based on the Wilson's Score method.

Corresponding methods will be used for other response rates (EoT response rate, relapse rate, viral breakthrough). The relapse rates will be estimated in patients of the CP analysis groups with EoT response and sufficient HCV RNA measurements post-treatment. Viral breakthrough rates will be estimated in all patients of the CP analysis groups, who have at least one undetectable HCV RNA measurement on-treatment and at least one on-treatment or EoT measurement thereafter.

Univariate logistic regression methods will be used to investigate the impact of the following explanatory covariates on SVR12:

- Key demographic information
- Mode of CHC infection
- HCV RNA level at baseline
- Most recent stage of liver fibrosis
- HCV genotype and subtype (if available)
- Type of treating institute
- Liver and/or CHC related co-morbidities
- Key clinical chemistry and hematology laboratory variables at baseline

Confidential Information

No use or disclose outside AbbVie is permitted without prior written authorization from AbbVie  
The Netherlands v 1.4 (26 March 2018). Protocol based on AbbVie shell protocol version 3.0 (22 April 2015) Page 37 of 65

- In treatment experienced patients only:
  - Most recent prior treatment for CHC
  - Outcome of most recent prior CHC treatment

Further details and additional covariates will be specified in the SAP.

These analyses will be of exploratory nature, data driven, and will be repeatedly performed for various CP Analysis Groups, since not each covariate might be predictive in each patient group. Logistic regression methods will also be used to investigate the impact of treatment adherence on SVR12.

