4.1.2 Secondary Parameters

The secondary effectiveness endpoints are:

- The percentage of patients with virological response (HCV RNA <50 IU/mL) at EoT (defined as last intake of ABBVIE REGIMEN or ribavirin)
- The percentage of patients with relapse (defined as HCV RNA <50 IU/mL at EoT followed by HCV RNA ≥50 IU/mL)
- The percentage of patients with breakthrough (defined as at least one documented HCV RNA <50 IU/mL followed by HCV RNA ≥50 IU/mL during treatment).
- Sustained virological response 24 weeks after EoT (SVR24, i.e. patients with HCV RNA < 50 IU/mL 24 weeks after EoT)
- The number and percentage of patients meeting each and any of the following SVR12 non-response categories:
 - On-treatment virologic failure (breakthrough [defined as above] or failure to suppress [each measured on-treatment HCV RNA value ≥50 IU/mL])
 - Relapse (defined as HCV RNA <50 IU/mL at EoT followed by HCV RNA ≥50 IU/mL post-treatment for subjects who complete treatment [not more than 7 days shortened])
 - Premature study drug discontinuation with no on-treatment virologic failure
 - Missing SVR12 data and/or none of the above criteria

Further secondary variables are:

- Type of treatment regimen (± Dasabuvir, ± RBV, intended and actual combination, dose and duration)
- Adherence
 - Percentage of the DAA dose taken in relation to the target dose of DAA (cumulative dose taken divided by target dose in percent)
 - Percentage of the RBV dose taken in relation to the target dose of RBV (cumulative dose taken divided by target dose in percent)
 - Percentage of missed RBV treatment days in relation to the target number of RBV treatment days
- Co-morbidities and concomitant medication
- Serious and non-serious adverse events and pregnancy occurrences

- Questionnaires on PROs: e.g. EuroQol 5 dimension 5 level (EQ-5D-5L) questionnaire and work productivity and activity impairment (WPAI) questionnaire prior to treatment initiation, at EoT as well as **12 and 24** weeks after EoT
- Healthcare resource utilization

No data will be imputed for any effectiveness or safety analyses except for the analyses of the HCV RNA endpoints and PRO questionnaires (if applicable). For further details see sections 4.2.3 and 4.2.7.2.2, respectively.

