4.2.7.2 Secondary Variables

4.2.7.2.1 Secondary Effectiveness Variables

Response

For the other response rates (i.e. SVR24, EoT response rate, relapse rate, viral breakthrough), the simple percentage of patients and a two-sided 95% confidence interval (CI) of the percentage will be computed (based on the Wilson's score method) as well. The EoT response rates will be reported for CP and the SVR24 rates will be reported for the respective CPSFU, stratified by genotype and cirrhosis status and overall. The relapse rates will be estimated stratified by SVR window (i.e. during SVR12 window=relapse₁₂, during SVR24 window=relapse₂₄, after SVR24

window=relapse_{late}) and stratified by genotype and cirrhosis status and overall in patients of the CP with EoT response who fulfilled the following criteria:

- completed treatment as defined previously,
- had at least one HCV RNA measurement ≥ 70 days post-treatment or was a treatment failure between EoT and 70 days post-treatment.

Viral breakthrough rates [defined as at least one documented HCV RNA <50 IU/mL followed by HCV RNA ≥ 50 IU/mL during treatment] will be estimated overall and stratified by genotype and cirrhosis status in all patients of the CP, who have at least one undetectable or unquantifiable, on-treatment HCV RNA measurement and at least one on-treatment or EoT measurement thereafter.

Non-Response

In another table, the numbers and the percentages of the SVR12 non-responder categories and responder will be summarized for CP patients, overall and stratified by genotype and cirrhosis status. The following SVR12 non-response categories will be considered:

- On-treatment virologic failure (breakthrough [defined as at least one documented HCV RNA <50 IU/mL followed by HCV RNA ≥ 50 IU/mL during treatment] or failure to suppress [each measured on-treatment HCV RNA value ≥ 50 IU/mL])
- Relapse (defined as HCV RNA <50 IU/mL at EoT followed by HCV RNA ≥ 50 IU/mL post-treatment and completed treatment as defined previously)
- Death and none of the above
- Premature study drug discontinuation with no on-treatment virologic failure and none of the above
- Insufficient virological response, other than those mentioned above (patients for whom insufficient virological response was reported, or who had HCV RNA ≥ 50 IU/mL post EoT) and none of the above
- Missing SVR12 data and/or none of the above criteria

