Virological response rates and non-response categories will be displayed for patients who completed treatment with ABBVIE regimen, as well.

SVR12 (Exploratory Analyses)

Univariate logistic regression methods will be used to investigate the impact of various explanatory covariates (patient and disease characteristics) at baseline on SVR12.

These analyses will be of exploratory nature, data driven, and will be performed for CP population.

The variables to be considered are as follows:

- Key demographic information
 - Age (continuous)

- Gender (Female [reference], Male)
 - Race/ethnic origin (White/Caucasian [reference], Black, Asian/Oriental, Other [all other races]); at least two categories with at least 10% of the patients each have to exists, so that this variable will be considered
 - Weight (continuous)
 - BMI (continuous)
 - IL28B, rs12979860 (CC [reference], CT or TT); patients with unknown genotype are excluded from the respective analyses.
- CHC disease characteristics
 - Years since diagnosis (continuous)
 - Mode of CHC infection (Drug use [reference], Other [all other answers excluding unknown], unknown);
 - Most recent stage of liver fibrosis (No cirrhosis/Transition to cirrhosis [reference], Cirrhosis; for definition see 4.2.6.2);
- HCV RNA level at baseline (\log_{10} IU/mL)
- HCV genotype(G1a*, G1b, G4; for definition see section 4.2.6.2)
- Type of treating institute (Private Practice / Private Hospital, Academic / University Hospital, General Hospital, Other)
- Co-infections (every patient not reporting the respective co-infection is considered as not having the respective co-infection)
 - HIV(No [reference], Yes)
 - HBV(No [reference], Yes)
- Liver and/or CHC related co-morbidities (every patient not reporting the respective co-morbidity is considered as not having the respective co-morbidity)
 - Liver transplantation (No [reference], Yes)
 - Steatosis (non-alcoholic) (No [reference], Yes)
 - Decompensated liver disease (No [reference], Yes)
- Other co-morbidities (every patient not reporting the respective co-morbidity is considered as not having the respective co-morbidity)
 - Depression (No [reference], Yes)
 - Diabetes mellitus (No [reference], Type 1/Type 2)
 - Hypertension (No [reference], Yes)
 - Immunologically mediated disease (No [reference], Yes)

- Hypothyroidism (No [reference], Yes)
- Alcohol use (None [reference], Yes –occasional, Yes –regular, Exdrinker)

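### The SAP's relapse analysis requires completed treatment, which its own endpoint and the protocol do not, so documented rebound after an early stop drops out of the Core Population relapse rate

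*SAP*

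**What the plan says.** **Endpoint.** The second bullet of SAP 4.1.2 is "The percentage of patients with relapse (defined as HCV RNA <50 IU/mL at EoT followed by HCV RNA ≥50 IU/mL". Protocol 9.7.3.2 gives the same definition. Neither mentions completion of treatment.

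**Denominator in the protocol.** Section 9.7.3.3: "The relapse rates will be estimated in patients of the CP analysis groups with EoT response and sufficient HCV RNA measurements post-treatment". Follow-up is required; completion is not.

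**Non-response category in the protocol.** Section 9.7.3.2 is wider than the endpoint: "Relapse (defined as HCV RNA <50 IU/mL at EoT or at the last on-treatment HCV RNA measurement followed by HCV RNA ≥50 IU/mL post-treatment".

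**Non-response category in the SAP.** The last bullet group of 4.1.2 limits relapse to completers: "for subjects who complete treatment [not more than 7 days shortened". Section 4.2.7.2.1 repeats the limit: "Relapse (defined as HCV RNA <50 IU/mL at EoT followed by HCV RNA ≥ 50 IU/mL post-treatment and completed treatment as defined previously".

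**Denominator in the SAP.** Section 4.2.7.2.1 takes CP patients with EoT response who completed treatment. They must also have an HCV RNA value at 70 days or later after treatment, or have failed between EoT and day 70.

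**Completer tables.** The SAP plans these separately: "Virological response rates and non-response categories will be displayed for patients who completed treatment with ABBVIE regimen, as well". Table 7 labels them as completer tables. The relapse-rate table has no such label, and its population is given as the Core Population.

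**The concern.** The analysis section does not estimate the endpoint that the SAP states. EoT is defined to include premature discontinuation (footnotes to protocol Table 2 and SAP Table 1), so an early stopper can be an EoT responder and can meet the relapse endpoint. The completion condition removes that patient from the relapse rate.

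The SAP announces other departures from the protocol: the upper bound of the SVR12 window, the added 48-week windows and the replacement of the shift tables. It does not announce this one. A reader of the output list would take a completer-only rate for a CP rate, and no listed table gives the rate that the protocol defines.

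This bears on the study's purpose. The study asks how trial results carry over to routine practice with varied compliance, and one secondary objective is the influence of adherence on outcome. Protocol 9.2.3 asks sites to complete the SVR12 and SVR24 pages, where data exist, for early terminators who responded. The relapse rate then leaves those data out.

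**Working it through.** The documents give no expected relapse or early-stop rate, and enrolment of 50-55 is stated not to rest on statistical considerations. There is no plan figure to reproduce. The check has two parts.

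**1. Where the patient goes.** Take an SVR12 non-responder who had HCV RNA below 50 IU/mL at EoT, has a documented later value of 50 or more, and had no on-treatment failure. The categories in SAP 4.2.7.2.1 run in this order: on-treatment failure; relapse (completers); death; premature discontinuation; insufficient response, which includes viremia after EoT; missing or other. Death, premature discontinuation and insufficient response each apply only if no higher category does.

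| Patient | Category in SAP 4.2.7.2.1 |
|---|---|
| Completed treatment | Relapse |
| Stopped more than 7 days early, alive | Premature discontinuation |
| Stopped more than 7 days early, died | Death |

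The category for viremia after EoT ranks below discontinuation, so it cannot receive the early stopper. The discontinuation row therefore pools documented rebound with early stoppers who have none.

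**2. Effect on the relapse rate.** Let *a* of *m* completers relapse and *b* of *e* early stoppers rebound, all with EoT response and adequate follow-up.

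- SAP rule: a/m
- Endpoint as defined: (a + b)/(m + e)

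The SAP rate is lower exactly when b/e > a/m. The interval is the planned Wilson 95% interval, with z = 1.96: centre (p + z²/2n)/(1 + z²/n), half-width z·√(p(1−p)/n + z²/4n²)/(1 + z²/n).

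Assumed for illustration: m = 47, a = 1, e = 3. The SAP rate is then 1/47 = 2.1% (0.4-11.1%) in every row.

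| Rebounds among 3 early stoppers | Endpoint as defined |
|---|---|
| 0 | 1/50 = 2.0% (0.4-10.5%) |
| 1 | 2/50 = 4.0% (1.1-13.5%) |
| 2 | 3/50 = 6.0% (2.1-16.2%) |

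With 55 responders and two rebounds: 1/52 = 1.9% (0.3-10.1%) against 3/55 = 5.5% (1.9-14.9%). With e = 0 the two rates are identical.

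A wider set of assumptions uses 50 or 55 responders and 0-2 completer relapses. Early stops and rebounds are paired as 1 and 1, 2 and 1, 3 and 2, or 5 and 3. The gap then runs from 1.7 points (2/53 = 3.8% against 3/55 = 5.5%) to 6.0 points (0/45 = 0% against 3/50 = 6.0%). Every case in this set has at least one rebound after an early stop, so it shows the size of the effect where there is one, not whether there is one.

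**The case against.** Five things can be said for the SAP.

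- **The limit on the category is stated openly.** The non-response bullet in SAP 4.1.2 already carries it. This stands: 4.2.7.2.1 does not introduce the category limit. It also means that 4.1.2 holds two relapse definitions, and the relapse-rate bullet still conflicts with its own analysis.
- **The rate need not be lower.** A reader might infer that the completer-only rate must flatter the regimen. The documents do not support that. With no rebounds among three early stoppers the SAP rate is marginally higher (2.1% against 2.0%). Protocol 7.1 describes a low discontinuation rate in Phase III, so there may be few early stoppers.
- **The failures are not hidden.** A reader might infer that these patients vanish. They do not. One whose rebound is seen by the SVR12 window is still an SVR12 failure. Early stoppers also appear in the premature-termination tables with reasons, and their shortened courses enter the adherence regression. For patients with no HCV RNA test at least 10 weeks after treatment, the recorded reasons for not completing the study include relapse. What is lost is the link between early stop and documented rebound, and the relapse rate itself.
- **The discontinuation category is the protocol's own.** True, but protocol 9.7.3.2 reports each and any category that applies, so this patient would count there as a relapse as well. The SAP's ranking together with the completion limit removes that.
- **Separating relapse after a full course from rebound after a short one is reasonable.** It is, if labelled and shown as a supplement.

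The table shells (SAP Part II) are not among the documents, so footnotes or row splits there cannot be checked.

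**Conclusion.** The point holds as an internal contradiction and an unflagged departure from the protocol in a secondary endpoint. SAP 4.2.7.2.1 estimates relapse among completers, while SAP 4.1.2 and the protocol define it without regard to completion. The comparison group is EoT responders with adequate follow-up, not all EoT responders, because the protocol also requires post-treatment HCV RNA data.

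The direction and size are open. The rate is understated only if early stoppers rebound more often than completers. The example of 2.1% against 6.0% rests wholly on assumed counts, and its intervals overlap widely. The effect may be nil. With 50-55 patients, however, one or two such cases visibly move the rate.

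The SVR12 result does not depend on this rule. A reader might also infer that the relapse rows of the all-CP and completer non-response tables are identical by construction. That is true of the counts only; the percentages have different denominators.

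**What to change.** 1. In SAP 4.2.7.2.1 delete the completion criterion from the main CP relapse rate. The denominator becomes all CP patients with EoT response who have at least one HCV RNA value at 70 days or later after treatment, or who failed between EoT and day 70. Show the completer-only rate beside it, labelled as such.
2. State that rebounds before day 70 count in the overall relapse rate, and in which window stratum they appear. The three planned strata (SVR12 window, SVR24 window, later) name no place for them.
3. In the all-CP non-response table, split both the premature-discontinuation row and the death row by whether HCV RNA of 50 IU/mL or more was documented after treatment in a patient with EoT response.
4. Align the relapse wording in 4.1.2 and 4.2.7.2.1. Flag any restriction that is kept as a departure from the protocol, as the SAP does for its other changes.

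The cost is SAP wording, one further relapse-rate display and a few table rows. No new data are needed. The main relapse rate may come out somewhat higher, slightly lower or unchanged.

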During the last decade when dual therapy with pegIFN plus RBV was standard of care for the treatment of CHC, management of patients and clinical outcome were improved following the discovery of predictive factors of virological response, often in observational studies with large data bases [66]. Thus treatment could be targeted to patients most likely to respond and futile treatment stopped in patients with a low likelihood of virological cure. HCV genotype and subtype, baseline viral load, fibrosis stage, age, treatment exposure and on-treatment virological response proved to be useful predictors for the eradication of HCV in everyday clinical practice [27]. The discovery of a genetic disposition of the Interleukin 28B (IL28B) single nucleotide polymorphism (SNP) contributed further to our understanding of virological responses to PegIFN and RBV regimen [67]. For new interferon-free treatment regimens knowledge of predictive factors of virological response is extremely sparse and several of the now well established predictors of response were not initially identified through analyses of the development trials. This observational study may play an important part in bridging the data gaps and could help identify predictive factors of virological response in everyday clinical settings which were not detected in interventional trials and which could be used to further optimize treatment with the interferon-free ABBVIE REGIMEN in the future.

The label of the ABBVIE REGIMEN will vary according to HCV genotype/subtype and stage of liver disease. It is therefore relevant to understand the pattern of use and outcome in daily clinical practice. In addition, this study will provide data on the impact of adherence on treatment outcomes in everyday settings, which may help treating physicians to improve the management of patients under their care.

The aim of this observational study is to provide evidence of the effectiveness, tolerability, adherence, healthcare resource utilization, quality of life and work productivity of the ABBVIE REGIMEN ± RBV in a real world setting across clinical practice patient populations.

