4.2.3 Handling of missing data

No data will be imputed for any effectiveness or safety analyses except for the analyses of the HCV RNA endpoints and certain PRO endpoints. The discussion of missing data imputation for the PRO endpoints is included in section 4.2.7.2.2.

HCV RNA values will be selected for an RVR, EOTR and SVR analysis based on visit windows as defined in Table 2. When there is no HCV RNA value in a visit window based on defined visit windows, the closest values before and after the window, regardless of the value chosen for the subsequent and preceding window, will be used for the flanking imputation described below. For

analysis of RVR, EOT and SVR, if a subject has a missing HCV RNA value at a post-Day 1 visit but with undetectable or unquantifiable (LLoD or LLoQ \leq 50 IU/mL) HCV RNA levels at both the preceding value and succeeding value, the HCV RNA level will be considered undetectable or unquantifiable, respectively, at this visit for this subject. In addition, if a subject has an unquantifiable HCV RNA level at the preceding value and an undetectable HCV RNA level at the succeeding value, or vice versa, the HCV RNA level will be imputed as unquantifiable at this visit for this subject.

For analyses of RVR, subjects still missing a value for the visit after flanking imputation will be considered as a failure. For EoTR and SVR analysis, if there is no value in the appropriate window after flanking imputation but there is an HCV RNA value after the window, then it will be imputed into the EoTR or SVR window respectively. Subsequent to this flanking and backward imputation, if the HCV RNA value remains missing at a specific time point, then the subject will be considered as virological failure at this time point (i.e., not undetectable or unquantifiable).

If a subject starts another treatment for HCV, then all HCV RNA values for this subject measured on or after the start date of the new HCV treatment will be excluded from analyses. The subject will be considered a failure for summaries of viral response at all time points after the start of the new HCV treatment.

Due to the non-interventional nature of this study several different methods for determination of the HCV RNA value can be applied. For the purpose of the statistical analysis, a HCV RNA measurement is considered <50 IU/mL,

- if a PCR test was used

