4.2.7 Analyses of the Objectives

4.2.7.1 Primary Effectiveness Variable

The primary objective of this study is to estimate the SVR12 rates in HCV patients treated according to the ABBVIE regimen.

Therefore the simple percentage of patients achieving SVR12 (for definition see section 4.1.1) will be calculated and a two-sided 95% confidence interval (CI) of the percentage will be computed based on the Wilson's Score method.

The primary effectiveness analysis on clinical outcomes will be performed on all patients in the CP stratified by genotype and cirrhosis status and overall.

In the framework of sensitivity analyses the primary analyses will be repeated for the CPSFU. Furthermore, the SVR12 rates will be also determined for all patients of the NCP.

An overview of Tables is given in Table 7.

The layouts of the tables mentioned above are provided in Part II of the SAP (Table Shells).

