In addition to the summary statistics of the adherence variables, logistic regression analyses will be performed for the following adherence variables: "adherence to ABBVIE regimen" in all patients of the CP, "adherence to ribavirin" in all patients of the CP taking RBV, each categorized as follows: >=95%, >80%-<=95%, <=80% to investigate the additional impact of overall treatment adherence on SVR12. The categories may be changed if they are sparsely filled. Adherence will be included as mandatory covariate in addition to the baseline explanatory variables already mentioned above. Also the same methods will be applied as described above.

An overview of Tables is given in Table 7.

Table 7 Overview of Outputs for Primary and Secondary Effectiveness Analysis

Output Title	Output Short Name	Analysis Population
Virological Response Rates by Genotype and Cirrhosis Status – CP/CPSFU - <country>	tvr_<c>_gc_cp	Core population/ Core population with sufficient follow-up data
Virological Response Rates by Genotype and Cirrhosis Status in Patients who Completed ABBVIE Regimen – CP/CPSFU - <country>	tvr_<c>_gc_cp_ARC	Core population/ Core population with sufficient follow-up data: patients who completed ABBVIE regimen
Virological Response Rates - NCP - <country>	tvr_<c>_ncp	Non-core population
Relapse Rates by Genotype and Cirrhosis Status – CP - <country>	trr_<c>_gc_cp	Core population
Viral Breakthrough by Genotype and Cirrhosis Status – CP - <country>	tvb_<c>_gc_cp	Core population
Non-Response Rates by Genotype and Cirrhosis Status – CP - <country>	tnrr_<c>_gc_cp	Core population
Non-Response Rates by Genotype and Cirrhosis Status in Patients who Completed ABBVIE Regimen – CP - <country>	tnrr_<c>_gc_cp_ARC	Core population: patients who completed ABBVIE regimen
Impact of Patient and Disease Characteristics on SVR12 – CP - <country>	tis_<c>_cp	Core population
Adherence by Genotype and Cirrhosis Status - CP - <country>	tah_<c>_gc_cp	Core population
Adherence by Treatment Regimen and Cirrhosis Status - SP - <country>	tah_<c>_tc_sp	Safety population
Impact of Adherence to ABBVIE Regimen on SVR12 – CP - <country>	tiaa_<c>_cp	Core population
Impact of Adherence to Ribavirin on SVR12 in patients taking RBV – CP - <country>	tiar_<c>_cp_RBV	Core population: patients taking RBV

The layouts of the tables mentioned above are provided in Part II of the SAP (Table Shells).

4.2.7.2.2 *Quality of life*

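### The SVR12 covariate and adherence regressions are planned only in the CP, where a still-missing SVR12 counts as failure; they should also be shown in the CPSFU, with the events broken down by type.

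*SAP*

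**What the plan says.** SAP 4.2.7.2.1 plans univariate logistic regressions of SVR12 on a long list of baseline covariates and fixes the population: "These analyses will be of exploratory nature, data driven, and will be performed for CP population". Protocol 9.7.3.3 likewise keeps these models within the CP analysis groups. SAP Table 7 lists one output for them, titled "Impact of Patient and Disease Characteristics on SVR12", for the CP. For the adherence models the SAP states: "Adherence will be included as mandatory covariate in addition to the baseline explanatory variables already mentioned above". Table 7 lists those two outputs (ABBVIE regimen, ribavirin) for the CP only.

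The outcome follows SAP 4.2.3. If a value exists only after the SVR12 window, "then it will be imputed into the EoTR or SVR window respectively". If the value is still missing after flanking and backward imputation, "then the subject will be considered as virological failure at this time point".

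For the primary rate, SAP 4.2.7.1 adds a check: "In the framework of sensitivity analyses the primary analyses will be repeated for the CPSFU". SAP 4.2.1 defines the CPSFU so that it drops responders with no later test for reasons unrelated to safety or effectiveness. No regression is planned in it.

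On purpose, Protocol 7.2 says the study "could help identify predictive factors of virological response in everyday clinical settings". SAP section 1 speaks more broadly of predictors of response in real-world treatment settings.

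**The concern.** Scoring missing as failure is a conservative rule for a response rate. For an odds ratio it has no fixed direction. The modelled event becomes a mixture of documented virologic failure and absence of a test. A covariate that acts only on attendance can then appear to predict non-response, and a covariate that acts on the virus is diluted by events that have nothing to do with it.

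The setting makes non-return realistic. HCV RNA testing is at the physician's discretion (Protocol 9.7.1, SAP 4.2.2), and failure to return is a listed reason for not completing the study (SAP 4.2.5). Mode of infection, alcohol use, depression and type of institute are among the listed covariates and could plausibly relate to attendance. Adherence is exposed by a second route. It is pills taken over pills planned, so early stoppers score low, and Protocol 9.2.3 asks for their SVR12 page only if data are available.

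**Working it through.** The plan gives no figure to reproduce: the sample size has no statistical basis, and no missing rate is stated. The check therefore reads the rules and works out their consequences over a range.

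**Inputs**
- N = 50-55 expected to enrol (SAP 3.2). The CP is a subset, so the counts below are upper values.
- s = SVR12 if everyone were tested, 90-97%. This is an assumption, in line with Protocol 7.1: 90-100% in Table 1 for patients without cirrhosis, 92% and 96% with cirrhosis.
- m = proportion with SVR12 still missing after imputation, 5-10%. This is an assumption.

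**Share of events that are only missing data**

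CP failure f = m + (1 - m)(1 - s); share = m / f.

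| s | m = 5% | m = 10% |
|---|---|---|
| 90% | 0.05/0.145 = 34% | 0.10/0.190 = 53% |
| 95% | 0.05/0.0975 = 51% | 0.10/0.145 = 69% |
| 97% | 0.05/0.0785 = 64% | 0.10/0.127 = 79% |

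In patients, missing values number 50 × 0.05 = 2.5 to 55 × 0.10 = 5.5. Virologic failures number 50 × 0.90 × 0.03 = 1.35 to 55 × 0.95 × 0.10 = 5.2.

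**Covariate with no virological effect, loss 10% versus 5% (assumed)**

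OR = [f1/(1 - f1)] / [f0/(1 - f0)].
- s = 90%: (0.190/0.810)/(0.145/0.855) = 1.38
- s = 95%: (0.145/0.855)/(0.0975/0.9025) = 1.57
- s = 97%: (0.127/0.873)/(0.0785/0.9215) = 1.71

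**Covariate with a real effect, equal loss**

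Take failure of 3% versus 8.49%, a true OR of 3.
- m = 5%: f = 0.0785 and 0.1307, OR 1.76
- m = 10%: f = 0.127 and 0.1764, OR 1.47

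**Same null covariate in the CPSFU**

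If loss is for reasons unrelated to safety or effectiveness, and unrelated to outcome, dropping the lost patients gives an expected OR of 1.00. The CPSFU keeps patients whose last value was ≥50 IU/mL even if they never return. If every failure were documented that way before loss, only lost responders would be removed, and the OR would be (1 - 0.05)/(1 - 0.10) = 1.06. Either way most of the artefact goes.

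**The case against.** The strongest reply has four parts.

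First, the analyses are univariate, labelled exploratory and data driven, and do not serve the primary objective. That limits the consequence but does not change what the odds ratios measure.

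Second, the size rests on assumptions. Backward imputation rescues anyone with a later test, so only patients who never return are affected. With virologic failure at 10% and 5% missing, the missing share is 34%, not 64%. This stands, and it is why a range is given.

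Third, a reader might infer that the SAP will report predictors of non-attendance as predictors of treatment failure. The documents do not support that. The output is titled as impact on SVR12, differential loss is not documented, and if loss is equal across levels the result is dilution, not a false predictor. SAP section 1 also allows external patient, provider and system factors into effectiveness, so non-return is partly within a real-world outcome. The non-response table separates death, discontinuation and missing data, so a reader can see the event mix, although this corrects no odds ratio.

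Fourth, it is tempting to make documented virologic failure the lead outcome, built from the SAP's non-response categories. Those categories do not serve. Relapse requires completed treatment, and premature discontinuation ranks above insufficient response. A patient who stops early, is below 50 IU/mL at EoT and later has HCV RNA ≥50 IU/mL is filed under discontinuation and would be lost as an event. Such a model would also be nearly empty: at 3% failure and 48-53 evaluable patients, the chance of no event at all is 0.97^53 = 20% to 0.97^48 = 23%.

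**Conclusion.** The concern holds as a gap in sensitivity analysis. The SAP protects the primary rate against missing SVR12 with the CPSFU but leaves the three sets of regressions without that check, although one stated purpose is to find predictors of virological response. Under assumed SVR12 of 90-97% and 5-10% missing, about one third to four fifths of modelled events would be missing data. Under assumed loss of 10% versus 5%, a null covariate would show an odds ratio of about 1.4-1.7. Wider assumed contrasts give larger values (5% versus 20% at s = 95%: 2.92), but nothing in the documents points to them. The documents do not show that the bias will occur, and they do not make the CP regressions wrong as a description of SVR12 under the study's own definition. It is a low-cost improvement to an exploratory analysis.

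**What to change.** Keep the CP regressions as planned. In SAP 4.2.7.2.1 and Table 7, add a repeat of the covariate regressions and of both adherence regressions in the CPSFU for SVR12, shown side by side with the CP results. In each table, report how many events are documented virologic failures and how many are death, discontinuation without virologic failure, or missing data. The counts matter most for adherence, because the CPSFU deliberately keeps patients untested for safety reasons as failures.

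If a virologic-failure outcome is also shown, define it as any documented on-treatment virologic failure, post-treatment HCV RNA ≥50 IU/mL or reported virologic failure, regardless of treatment completion. Do not build it from the hierarchical non-response categories.

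The cost is SAP wording and additional outputs, with no new data. State two limits in the SAP. With about 1 to 5 virologic events, estimates will be very imprecise or not estimable. Leaving out lost patients also assumes that their loss is unrelated to outcome.
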